#### 10.3 Correlatives

We propose a series of correlative studies to evaluate for pre-treatment and post-treatment predictors of response or resistance to pembrolizumab in ENKTL:

# **Tissue biopsies**

Pre-treatment biopsies will be required prior to initiation of study treatment unless archival tissue is available. On-treatment biopsies will be performed during Cycle 1 (between days 8-20), except in cases where due to the location of disease, biopsy would be associated with unnecessary risk to the patient. In addition, biopsies will be performed after 4 cycles of pembrolizumab for patients who do not achieve complete metabolic response. Tissue will be collected, processed, and stored for planned correlative studies including;

- 1. **Immunohistochemistry** for MHC-I, MHC-II, B2M, PD-1, PD-L1, PD-L2, FoxP3, CD68, CD4, and CD8 to evaluate for both cell autonomous and non-cell autonomous markers of immune evasion and elucidate mechanisms of action.
- 2. Molecular profiling by MSK IMPACT assay to evaluate for mutations and altered expression profiles associated with disease response and resistance. In most cases, patients will have this as done as part of their clinical workup.

#### **Blood Collection**

Additionally, based upon prior reports regarding the prognostic and predictive value of plasma EBV DNA levels in ENKTL, we will evaluate EBV DNA levels by PCR at baseline and during therapy to clarify its significance for patients with ENKTL treated with checkpoint inhibitors. We are collecting blood for analysis of EBV DNA levels by PCR at baseline, C2D1, C4D1, and then odd cycles starting Cycle 5. Following completion of treatment, EBV PCR will be evaluated every 3 months for 3 years.

#### **Cell-free DNA**

Cell-free DNA (cfDNA) will be extracted from serum samples obtained at C1D1, C1D4, after completion of SMILE or C5D1 of pembrolizumab, EOT, and 6 months, 1 year and 2 years into follow-up or until a new therapy is initiated. Shallow whole genome sequencing be used to detect copy number alterations in order to confirm tumor vs host origin and quantify tumor-specific cell-free DNA. Targeted resequencing using the MSKCC HemePACT assay will be performed on cell-free DNA to identify genomic alterations present at baseline, on treatment, and in follow-up.

#### 10.4 MSK IMPACT Testing

The consent indicates that samples and genetic information collected may be shared with other qualified researchers and placed in online databases. An example of an online database is the NIH dbGAP database, which is monitored by the National Institutes of Health, and may be made accessible to investigators approved by the U.S. government.

Such information will not include identifying information such as name. It is also stated in the Research Authorization that research data (e.g. genomic sequence) may be shared with regulators. The requirements for submission of genotype/phenotype data into the NIH dbGAP or any other public database will be followed as per the MSK IRB SOP for Genomic Data Sharing.

In the course of this research it is possible that some patients whose tumors are analyzed through investigational "next-generation" profiling in a research (non-CLIA) environment will be found to have somatic or germline mutations in genes that are known to be associated with an increased risk of cancer or other diseases. It will be stated in the consent that the participants will not receive any specific results from research tests. The consent will tell participants that if they wish to have genetic testing done for personal reasons than they should make an appointment with the MSK Clinical Genetics Service or Clinical Genetics Service at their site.

If in the course of this research a research finding is obtained that, in the opinion of the investigator, may be critical to the preventive care of the participant or their family, the investigator can communicate that finding to the MSK IRB Genomic Advisory Panel (GAP). The finding will be reviewed by the GAP to determine whether the incidental finding should be discussed with the participant. For MSK patients, in the event that the GAP determines that the finding should be discussed with the participant, and the participant has consented to be re-contacted, then the treating/consenting physician shall be contacted by the panel and asked to refer the participant to the Clinical Genetics Service for further discussion of the research finding.

The following information must be provided to GAP for review:

- Participant Name/MRN #
- Type of Biospecimen (tissue, blood, saliva)
- Incidental Finding
- Collection Protocol #
- Contact: [contact]

For non-MSK patients being treated at one of the participating institutions, in the event the GAP determines that the finding should be discussed with the participant, and the participant has consented to be re-contacted, the findings will be returned to the Site Principal Investigator. Site policies on returning these research findings to the patient should be followed.

# 10.5 Future Unspecified Use of Biospecimens

The protocol includes an informed consent document and research authorization that meets statutory guidelines. Each participating site will have its own consent form meeting the requirements described in this section. The consent form will inform patients of the purpose of the bank, their rights in relation to it, and the safeguards in place to protect the

confidentiality of their health information. The consent will state that some of the biospecimens will be saved to use for future research.

# Type of future use

The consent specifically describes the types of future research that may be performed, including use of tissues to develop new drugs with cancer-associated molecular targets, development of cell lines, future use of cell lines to define cancer phenotype and (somatic) genotype, DNA sequence analysis of tumor compared to normal and identification of tumor-associated proteins as diagnostic or prognostic markers. It will be stated that researchers at MSK may either keep indefinitely or dispose of any leftover blood or tissues or other samples, including DNA that the samples contain. Blood and tissues will be stored with identifiers in secure tissue or fluid banks. It is stated that the samples could be lost or ruined because of mechanical failure, and that MSK cannot guarantee that samples will be stored indefinitely. The samples will be stored for as long as deemed useful for research purposes.

# Consent for future use and re-contact

Patients are asked in a series of check boxes at the end of the consent if 1) they permit their biospecimen samples to be stored and used in future research to learn about or prevent cancer or side effects of treatment, or to develop new treatments; 2) if they permit their samples to be stored and used in future research to learn about, prevent, or treat diseases other than cancer; or 3) if they permit their samples, with personal identifiers protected, to be used for research about inherited genetic factors, 4) if they permit their samples to be used for genetic analysis of the tumor and normal tissue to learn about the causes of cancer, 5) participants are asked if they agree to be contacted in the future as part of research studies for additional health information or to be asked to participate in future biospecimen research studies and 6) if they consent to be contacted to discuss research findings which may come from their sample. Finally, if not available (e.g. deceased), if they wish to have their designee designated on the consent to be contacted.

Participants will not be provided with specific results of research tests performed on their collected human biologic specimens.

# Use of identifiable information for genetic studies

In the course of this research it is possible that some patients whose tumors are analyzed through investigational "next-generation" profiling in a research (non-CLIA) environment will be found to have somatic or germline mutations in genes that are known to be associated with an increased risk of cancer or other diseases. It will be stated in the consent that the participants will not receive any specific results from research tests. The consent will tell participants that if they wish to have genetic testing done for personal reasons than they should make an appointment with the MSK Clinical Genetics Service or Clinical Genetics Service at their site.

If in the course of this research a research finding is obtained that, in the opinion of the investigator, may be critical to the preventive care of the participant or their family, the investigator can communicate that finding to the MSK IRB Genomic Advisory Panel (GAP). The finding will be reviewed by the GAP to determine whether the incidental finding should

be discussed with the participant. For MSK patients, in the event that the GAP determines that the finding should be discussed with the participant, and the participant has consented to be re-contacted, then the treating/consenting physician shall be contacted by the panel and asked to refer the participant to the Clinical Genetics Service for further discussion of the research finding.

The following information must be provided to GAP for review:

- Participant Name/MRN #
- Type of Biospecimen (tissue, blood, saliva)
- Incidental Finding
- Collection Protocol #
- Contact: [contact]

For non-MSK patients being treated at one of the participating institutions, if the GAP determines the finding to be reportable to the participant and the participant has consented to be re-contacted, results will be returned to the Site Principal Investigator via the study team. Site policies on returning these research findings to the patient should be followed.

We anticipate that other research assays may be incorporated into this protocol as technology evolves.

# Voluntariness of research participation

It is stated that taking part in this tissue and blood bank is voluntary and patients have the right to withdraw at any time. Participation in the study will not impact on the clinical care patients receive.

#### Withdrawal

Participants may decide at a later date that they do not want identified blood and tissue samples to be stored in the tissue bank and /or used for future research. If participants decide to withdraw from the study, specimens that have not yet left the specimen archive will not be used in new studies and any remaining portions of samples that have not been used for research will be used only for clinical purposes or, if requested by the patient, destroyed. For specimens already shipped out from the archive, it may not be possible to locate the samples or stop already ongoing research. When a participant withdraws from the protocol, the MSK study team should be notified immediately. If a non-MSK participant withdraws from the study, the MSK study staff member will notify the MSK database teams. The withdrawal request will be documented in CRDB and the system updated accordingly. In addition, a note-to-file documenting the patient withdrew must be filed in his/her medical records.

#### Rights after death

The consent states that if the research participant dies or is unable to make his/her wishes known, all of their rights to decide about future uses of the blood or tissues will pass to the authorized representative of the estate. If there is no representative of the estate, the rights pass to the next of kin.

# Risks of research participation

The greatest risk is release of information from health or research records in a way that violates privacy rights. MSK and any participating sites will protect records so that name, address, phone number, and any other information that identifies the participant will be kept private. It will be stated to the participant that the chance that this information will be given to an unauthorized individual without the participant's permission is very small.

# Costs/compensation

There is no cost to the participant to enroll in this research. Tissue or blood obtained in this research may be used to make a cell line, and these may be patented or licensed and thus may have significant commercial value. The participant is informed that there are no plans to provide financial compensation for use of their human biologic specimens, nor are there plans for the participant to receive money for any new products, tests, and discoveries that might come from this research.

# Biospecimen Privacy

Medical information is confidential. The participant's personal identity will not be used in reports that are written about the research. The MSK IRB/PB will review all requests for research performed involving biospecimens ascertained through this protocol. Blood and tissue samples may be stored with a code linked to the patient's medical record. The results of any research using blood or tissues will not be placed in the medical record.

The consent indicates that samples and genetic information collected may be shared with other qualified researchers and placed in online databases. An example of an online database is the NIH dbGAP database, which is monitored by the National Institutes of Health, and may be made accessible to investigators approved by the U.S. government. Such information will not include identifying information such as name. It is also stated in the Research Authorization (HIPAA Authorization) that research data (e.g. genomic sequence) may be shared with regulators. The requirements for submission of genotype/phenotype data into the NIH dbGAP or any other public database will be followed as per the IRB SOP for Genomic Data Sharing.

# Use of banked samples (at MSK)

When samples are to be analyzed, the individual investigator needs to write an IRB biospecimen protocol. This protocol is fast-tracked through MSK Research Council review and is reviewed at the MSK IRB by the expedited review process. This protocol is only for research that will be done on biospecimens obtained under identified protocols and their informed consent and research authorization that include the institutional future use questions. The consent and research authorization for the use of the biospecimens will be waived as per 45 CFR 46.116(d) and 45 CFR 164.512(i)(2)(ii).

# 11.0 TOXICITIES/SIDE EFFECTS

# 11.1 Adverse Events Definitions

An AE is any untoward medical occurrence in a study subject and does not necessarily have a causal relationship with this treatment.

An AE therefore can be any unfavorable and unintended sign (including laboratory finding), symptom or disease temporally associated with participation in an investigational study, whether or not considered drug-related. In addition to new events, any increase in the severity or frequency of a pre-existing condition that occurs after the subject signs a consent form for participation is considered an AE. This includes any side effect, injury, toxicity, or sensitivity reaction.

Whenever possible, the Common Terminology Criteria for Adverse Events (CTCAE) version 4.0 should be used to describe the event and for assessing the severity of AEs. Any events representing a change in the CTCAE Grade need to be reported in CRDB. This includes any change in laboratory values.

For AEs not adequately addressed in the CTCAE, the severity table (Table 5.0) below may be used:

**Table 5.0 AE Severity Table** 

Severity	Description
GRADE 1 – Mild	Transient or mild discomfort; no limitation in activity; no medical intervention/therapy required.
GRADE 2 – Moderate	Mild to moderate limitation in activity—some assistance may be needed; no or minimal medical intervention/therapy required.
GRADE 3 – Severe	Marked limitation in activity, some assistance usually required; medical intervention/therapy required, hospitalizations possible.
GRADE 4 – Life-threatening	Extreme limitation in activity, significant assistance required; life-threatening (immediate risk of death); significant medical intervention/therapy required, hospitalization or hospice care probable.
GRADE 5 – Fatal	Death

Any condition, laboratory abnormality, or physical finding with an onset date prior to the subject signing consent for study participation is considered to be pre-existing in nature and part of the subject's medical history.

# 11.2 Causality

Using the following criteria, the relationship of the AE to the study drug should be assessed as follows:

- Yes: The event is suspected to be related if:
  - There is a clinically plausible time sequence between onset of the AE and administration of study treatment; and/or
  - There is a biologically plausible mechanism for the study treatment to cause or contribute to the AE; and/or

- The event responds to withdrawal of the study intervention (dechallenge) and/or recurs with rechallenge (when clinically feasible); and/or
- The AE cannot be reasonably attributed to concurrent/underlying illness, other drugs, or procedures

#### No:

- The AE is more likely to be explained by the subject's clinical state, underlying disease, concomitant medication, study or non-study procedure; and/or
- The time of occurrence of the AE is not reasonably related to administration of study treatment; and/or
- The event is unlikely to be related to the investigational procedures(s)

# 11.3 Adverse Events Reporting Procedures

All AEs (e.g., any new event or worsening in severity or frequency of a pre-existing condition or laboratory finding) with an onset date after the subject signs consent for study participation must be promptly documented on the appropriate summary. Details of the event must include severity, relationship to study drug, duration, action taken, and outcome.

All AEs that are considered related to study procedures must be followed to resolution or stabilization if improvement is not expected.

AEs should be reported from the time the subject signs consent through 30 days post-last study intervention. In addition, the Investigator should report any AE that may occur after this time period that is believed to have a reasonable possibility of being associated with study intervention. If a subject discontinues study prior to receiving any study intervention, AEs must be reported through the end-of-study visit. AEs which completely resolve and then recur should be recorded as a new AE. For subjects who complete the end of study visit less than 30 days following the last study intervention, a follow up of ongoing AEs should be attempted by telephone and documented in the subject's source. AEs continuing at 30 days post-last treatment should have a comment in the source by the Investigator that the event has stabilized or is not expected to improve.

The Principal Investigator is responsible for evaluating all AEs, obtaining supporting documents, and determining that documentation of the event is adequate. Adverse events will be assigned a severity grade using the NCI CTCAE grading scale v4.0 and recorded. Furthermore, the occurrence of grade 2 or higher immune-related adverse events will be collected and designated as immune-related events of clinical interest (irAEs).

# 11.4 Pembrolizumab side effects and supportive care

Refer to package insert for frequency of side effects

# 11.5 Dose Modification and toxicity management for immune-related AEs associated with pembrolizumab

AEs associated with pembrolizumab exposure may represent an immunologic etiology. These immune-related AEs (irAEs) may occur shortly after the first dose or several months after the last dose of pembrolizumab treatment and may affect more than on body system simultaneously. Therefore, early recognition and initiation of treatment is critical to reduce

complications. Based on existing clinical study data, most irAEs were reversible and could be managed with interruptions of pembrolizumab, administration of corticosteroids and/or other supportive care. For suspected irAEs, ensure adequate evaluation to confirm etiology or exclude other causes. Additional procedures or tests such as bronchoscopy, endoscopy, skin biopsy may be included as part of the evaluation. Based on the severity of irAEs, withhold or permanently discontinue pembrolizumab and administer corticosteroids. Dose modification and toxicity management guidelines for irAEs associated with pembrolizumab are provided in Table 6.

# Table 6 Dose modification and toxicity management guidelines for immune-related AEs associated with pembrolizumab

#### **General instructions:**

- 1. Corticosteroid taper should be initiated upon AE improving to Grade 1 or less and continue to taper over at least 4 weeks.
- 2. For situations where pembrolizumab has been withheld, pembrolizumab can be resumed after AE has been reduced to Grade 1 or 0 and corticosteroid has been tapered. Pembrolizumab should be permanently discontinued if AE does not resolve within 12 weeks of last dose or corticosteroids cannot be reduced to ≤10 mg prednisone or equivalent per day within 12 weeks.
- **3.** For severe and life-threatening irAEs, IV corticosteroid should be initiated first followed by oral steroid. Other immunosuppressive treatment should be initiated if irAEs cannot be controlled by corticosteroids.

Immune-related AEs	Toxicity grade or conditions (CTCAEv4.0)	Action taken to pembrolizumab	irAE management with corticosteroid and/or other therapies	Monitor and follow-up
Pneumonitis	Grade 3 or 4, or recurrent Grade 2	Withhold  Permanently discontinue	Administer corticosteroids (initial dose of 1-2 mg/kg prednisone or equivalent) followed by taper.  Add prophylactic	
 
Monitor participants for signs and symptoms of pneumonitis
 
Evaluate participants with suspected pneumonitis with
 

			antibiotics for opportunistic infections.	radiographic imaging and initiate corticosteroid treatment
Diarrhea / Colitis	Grade 2 or 3	Withhold	Administer     corticosteroids     (initial dose of     1-2 mg/kg     prednisone or     equivalent)     followed by	Monitor participants for signs and symptoms of enterocolitis (i.e., diarrhea, abdominal pain, blood or mucus in stool with or without
	Recurrent Grade 3 or Grade 4	Permanently discontinue	taper	fever) and of bowel perforation (i.e., peritoneal signs and ileus).
				• Participants with ≥ Grade 2 diarrhea suspecting colitis should consider GI consultation and performing endoscopy to rule out colitis.

				Participants with diarrhea/colitis should be advised to drink liberal quantities of clear fluids. If sufficient oral fluid intake is not feasible, fluid and electrolytes should be substituted via IV infusion.
AST / ALT elevation or Increased bilirubin	Grade 2 ª	Withhold	Administer     corticosteroids     (initial dose of         0.5- 1 mg/kg     prednisone or     equivalent)     followed by     taper	Monitor with liver function tests (consider weekly or more frequently until liver enzyme value returned to baseline or is stable
	Grade 3 b or 4 c	Permanently discontinue	Administer     corticosteroids     (initial dose of 1-     2 mg/kg     prednisone or     equivalent)     followed by     taper	
Type 1 diabetes mellitus (T1DM) or Hyperglycemia	Newly onset T1DM or Grade 3 or 4 hyperglycemia associated with evidence of β-cell failure	Withhold d	Initiate insulin replacement therapy for participants with T1DM     Administer antihyperglycemic in participants with hyperglycemia	Monitor participants for hyperglycemia or other signs and symptoms of diabetes.
Hypophysitis	Grade 2 Grade 3 or 4	Withhold	Administer corticosteroids and initiate	Monitor for signs and symptoms of hypophysitis
	Grade 3 or 4	Withhold or permanently discontinue d	hormonal replacements as clinically indicated.	(including hypopituitarism and adrenal insufficiency)
Hyperthyroidism	Grade 2	Continue	Treat with non- selective beta- blockers (e.g.,	Monitor for signs and symptoms of thyroid disorders.
TT 4 19	Grade 3 or 4	Withhold or permanently discontinue d	propranolol) or thionamides as appropriate	
Hypothyroidism	Grade 2, 3, or 4	Continue	Initiate thyroid     replacement     hormones (e.g.,     levothyroxine or     liothyroinine)	Monitor for signs and symptoms of thyroid disorders.

			per standard of care
Nephritis grading according to increased creatinine or acute kidney injury	Grade 2 Grade 3 or 4	Withhold  Permanently discontinue	Administer corticosteroids (prednisone 1 to 2 mg/kg or equivalent) followed by taper.      Monitor changes of renal function      renal function
Neurological Toxicities	Grade 2 Grade 3 or 4	Withold  Permanently Discontinue	Based on severity of AE, administer corticosteroids      Based on evaluation to confirm etiology and/or exclude other causes
Myocarditis	Grade 1 Grade2, 3 or 4	Withhold  Permanently discontinue	Based on severity of AE administer corticosteroids      Based on evaluation to confirm etiology and/or exclude other causes

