#### Administration

Pembrolizumab should be administered on Day 1 of each cycle after all procedures/assessments have been completed as detailed on the Schedule of Assessments (Section 10.0). Study treatments will be administered on an outpatient basis. Study treatment may be administered up to 3 days before or after (+/- 3 days) the scheduled Day 1 of each cycle. Subjects may be dosed with pembrolizumab no less than 17 days from the previous dose. Treatment related toxicity requiring treatment delay of 6 weeks or more would require removal from the study unless after discussion with the PI it is felt to be clinically appropriate for the patient to remain on study.

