#### 9.5 Involved site radiation

Patients with stage I or II disease will undergo involved site radiation therapy (ISRT) according to published ILROG guidelines for using ISRT for extranodal lymphomas.  A total dose of 45 Gy (25 daily treatments) will be given with the option of increasing it to 50.4 Gy (28 daily treatments) for patients who have PET-positive disease after pembrolizumab. Involved site radiation therapy will begin 2-6 weeks following cycle 4 of pembrolizumab. Cycle 5 of pembrolizumab will begin 3-6 weeks following completion of radiation. Patients with advanced stage disease may receive ISRT if indicated. ISRT may be administered between cycles of SMILE or after SMILE and will be performed according to institutional standards.

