# 10.0 EVALUATION DURING TREATMENT/INTERVENTION

# 10.1 Evaluations during treatment for stage I, II patients:

# Study Calendar, Stage I, II

Assessment Period	Screening 	Сус	le 1	Сус	le 2	ıf	Cycle 3	Сус	cle 4	In	Cycles 5	- Cycle 12	Post-Trea	atment
Study Days	Day -28 to 1	Day 1	Day 8-20	Day 1	Day 14- 21	PD	Day 1	Day 1	Day 14-21	volve		Day 14-21	End of Treatment	Follow up 
Visit Window 	-28 days	- 3 days		+/- 3 days		with n mothe	+/- 3 days	+/- 3 days	+/- 3 days	d Site				+/- 1 month
Informed consent	Х					no c erap				R				
Medical History	Х					< =				adi				
Review of concomitant medications		Х		Х		nical i and IS	Х	Х		ation	Х		Х	
Review of adverse events		Х		Х		l imp	Х	Х		Τh	Х		Х	
Physical Examination 		Х		Х		(Involved footnote	Х	Х		O O	Х		Х	Х
Vital Signs 		Х		Х		em lvo	Х	Х		rapy (ISF footnote	Х		Х	Х
ECOG/KPS		Х		Х		len lve	Х	Х		ot (E	Х		Х	Х
Hematology  and Chemistry 		Х		Х		t, proc d Site e 16]	Х	Х		7T)			Х	Х
HIV, Hepatitis B and Hepatitis C 	х					ᄁᅋ				OR SI				
Pregnancy test 8		Х				ed to 2 adiatio				 				
EBV PCR 9		Х		Х		2 c ion		Х		'n	Х		Х	Х
Referral to radiation oncology	х					ycles of Therapy				then				
FDG-PET/CT simulation 	Х					s of				ISR				
MRI nasal cavity (only for patients with nasal cavity disease)	х					SMILE y (see				T [see				
ECHO	Х													

ECG	Х											
Pulmonary function tests 11	Χ											
Baseline Biopsy or archive tissue 12	Х											
Research Tumor Biopsy 13			Х					X 				
PET/CT	X 				Х			Х		Cycle 8 & Cycle 12 	X	Х
Tumor assessment 14					Х			Х		Cycle 8 & Cycle 12		
cfDNA 		Х					Х		Х		Х	X 
Pembrolizumab 		Х		Х		Х	Х		Х			

- 1. Each cycle is 21 days in length.
- 2. **Screening assessments** must be completed prior to initiation of treatment. HIV, Hep B and C tests must be done within 6 months of start of treatment. Baseline biopsy must be done prior to treatment. All other assessments must be done within 28 days of treatment, except for laboratory tests which must be done within 14 days of treatment. Lab tests CBC and comp must be repeated within 3 days of C1D1. Pregnancy test is required for females of child-bearing potential and must be done within 7 days of initiating treatment.

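### Sections 9.3 and 13.0 take patients with toxicity off the study, not only off pembrolizumab, and nothing continues their PFS and OS follow-up

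*Combined protocol and SAP*

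**What the plan says.** Three places deal with stopping for toxicity.

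- Section 11.5, Table 6, General instruction 2 concerns the drug: "Pembrolizumab should be permanently discontinued if AE does not resolve within 12 weeks of last dose". It does not mention leaving the study.
- Section 9.3, Administration, concerns the study: "Treatment related toxicity requiring treatment delay of 6 weeks or more would require removal from the study". It then allows an exception: "unless after discussion with the PI it is felt to be clinically appropriate for the patient to remain on study".
- Section 13.0 says that patients are followed on study until progression or for 2 years after treatment ends. It then lists who is removed from study, and that list includes patients with unacceptable toxicity, a term it does not define.

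Elsewhere the protocol keeps the two ideas apart. In Section 9.1, early-stage patients who progress to stage III or IV leave treatment. In Section 9.2, advanced-stage patients with lymphoma on biopsy leave the study.

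Section 2.0 makes 2-year PFS and OS secondary objectives. Section 14.0 estimates both by Kaplan-Meier, separately for early and advanced stage, and gives no censoring rule. The study calendars in Sections 10.1 and 10.2 already schedule post-treatment imaging every 6 months for 2 years.

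**The concern.** Removal from study differs from discontinuing a drug. Section 13.0 sets removal against being followed on study, and no section restores follow-up for those removed. A site that follows the text could stop collecting progression and survival data on a patient whose only problem was toxicity.

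Kaplan-Meier estimation assumes that censored patients have the same later risk as those who remain. Patients removed for toxicity have lost pembrolizumab and may differ in prognosis in either direction. In groups this small, one such patient visibly moves the curve, and the missing follow-up cannot be recovered at analysis.

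**Working it through.** **Inputs.** Total enrolment of 19 and an expected 66% early stage are from Section 14.0. The event counts below are illustrative, because the plan states no expected PFS for this treatment and there is no figure of its own to reproduce.

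**Group sizes.** Early stage: 0.66 × 19 = 12.5, so about 12-13. Advanced stage: 19 − 12.5 = 6.5, so about 6-7.

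**Effect of one removal.** Take n patients, of whom one is removed for toxicity and d others later have an event, with no other censoring before 2 years.

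- Censored before the first event: S = 1 − d/(n − 1)
- Followed, no event: S = 1 − d/n
- Followed, event: S = 1 − (d + 1)/n

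| Group | Censored at removal | Followed, no event | Followed, event |
|---|---|---|---|
| Early, n = 12, d = 4 | 1 − 4/11 = 63.6% | 1 − 4/12 = 66.7% | 1 − 5/12 = 58.3% |
| Advanced, n = 6, d = 4 | 1 − 4/5 = 20.0% | 1 − 4/6 = 33.3% | 1 − 5/6 = 16.7% |

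**Sensitivity to timing.** If the early-stage removal comes after two of the four events, S = (10/12) × (7/9) = 64.8%. If it comes after all four, S = 8/12 = 66.7%, the same as for a patient followed without an event.

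**Side calculation on the Table 6 clock.** Section 9.5 says "Involved site radiation therapy will begin 2-6 weeks following cycle 4 of pembrolizumab" and "Cycle 5 of pembrolizumab will begin 3-6 weeks following completion of radiation". The dose arithmetic reproduces: 45 Gy / 1.8 Gy = 25 fractions. Fractions per week are not stated; 5 is assumed, which makes about 5 weeks.

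- Cycle 5 due, earliest: 2 + 5 + 3 = week 10 after cycle 4. Latest: 6 + 5 + 6 = week 17.
- In exact days, 25 fractions from a Monday span 33 days (4.7 weeks), giving 9.7 to 16.7 weeks. At 7 fractions per week (25/7 = 3.6 weeks) the range is 8.6 to 15.6.
- Time left under Table 6 when cycle 5 falls due: 12 − 10 = 2 weeks at best, 12 − 17 = −5 weeks at worst.
- Onset decides who is affected. An event that starts 2 weeks after cycle 4 has 12 − 2 = 10 weeks to resolve, with or without the break. One that starts in week 13 has none.

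**The case against.** The best defence is that the protocol does not mean to lose these patients. Section 13.0 opens with a follow-up commitment, the calendars contain a follow-up schedule, Table 6 speaks only of stopping drug, and Section 9.3 lets a patient stay after discussion with the PI. Unacceptable toxicity is undefined and need not cover every Table 6 stop. Section 14.0 does not say that removed patients are censored. The example also puts the removal before every event, whereas the scans after cycles 2 and 4 may already have recorded early progressions.

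Much of this stands. It makes censoring an assumption, keeps the number affected small and, as the timing check shows, shrinks the effect when removal is late. It does not close the gap: Section 9.3 makes removal the default, Section 13.0 uses the word study where other sections use treatment, and no text keeps a removed patient in follow-up.

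Two stronger readings are tempting. First, a reader might infer that the 6-week and 12-week rules conflict. They govern different things, study participation and drug. In 3-weekly dosing a 6-week delay counted from the due date falls at 3 + 6 = week 9, before the week-12 limit, so both can be applied. Second, a reader might infer that the planned radiotherapy break turns Table 6 into a forced stop for any immune-related event that withholds cycle 5. The documents do not support that. An event that starts early in the break has the same time to resolve as it would without one, Section 11.5 calls Table 6 guidelines, and Grade 3-4 endocrine events have their own resumption rule.

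**Conclusion.** The point holds as a minor weakness in follow-up. As written, Sections 9.3 and 13.0 allow a toxicity stop to end PFS and OS data collection. With about 12-13 and 6-7 patients per curve, one early removal can put the 2-year estimate several percentage points from what full follow-up would show: 63.6% against 66.7% or 58.3% in the early-stage example.

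This rests on three assumptions: removal ends outcome data collection, such patients are censored at removal, and the removal comes early. The documents give no rate of toxicity removals, so no expected number is claimed. The conclusion also rests on the protocol body; the listed appendices are not reproduced in the document.

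A reader might infer that the primary CR rate is compromised too. That is not shown. Section 14.0 counts patients removed before the first response evaluation as non-responders, and a problem at cycle 5 arises after the cycle 4 assessment.

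The Table 6 clock is a secondary note. For a resumable event that begins late in the planned break, little or no time may be left before the 12-week limit. Whether to change that is a clinical judgement about a safety stop and is not a required correction.

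**What to change.** Amend Sections 9.3 and 13.0 so that stopping for toxicity ends pembrolizumab only. State that response assessment and follow-up for PFS and OS continue on the existing schedule, including imaging every 6 months for 2 years, unless the patient withdraws consent to follow-up.

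The cost is amendment text, plus the already planned visits and scans for the few patients who would otherwise leave. No patients are added.

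For clinical discussion only: consider whether Table 6 should say how its 12 weeks are counted when an event begins late in the break before cycle 5. Counting from onset would move the limit later (onset at week 16 gives 16 + 12 = week 28) and so relax a safety stop. It should not be adopted on statistical grounds.
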